Outcome measures Primary outcome: Difference between MLP and KTFS in the change in interpalpebral fissure during and spontaneous blinking

Secondary outcome: Difference between MLP and KTFS in the changes in interpalpebral fissure during opening and volitional blinking

Secondary outcome: Proportion of subjects selecting each device at the end of the crossover

Population: Individuals with severe unilateral or bilateral ptosis defined as occlusion of the visual axis by the lid in the resting state

[figure not shown]
Phase: N/A

Clinical Trial to improve the magnetic levator prosthesis (MLP) including the development and testing of a novel adjustable force system and comparison to the Kinesio Tape frontalis sling (KTFS) Version 1

Number of Sites enrolling participants:	1
Description of Study Agent :	Magnetic levator prosthesis (MLP) with compatible spectacle frames
Study Duration:	Kinesio Tape frontalis sling (KTFS)
Participant Duration:	2 to 3 years
	8 or 9 weeks from enrollment to the end of the crossover period of the clinical trial, with an additional 8 weeks after the end of the crossover for subjects who have a clinical decision to participate in the extended wear part of the clinical trial

SCHEMATIC OF STUDY DESIGN

Also, please refer to the study schema:

FU: Follow up

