10.2 Statistical Hypotheses

Primary outcome measure:

Statistics for the participant characteristics will be presented in terms of mean \pm standard deviation or median \pm interquartile range (25th to 75th). Within subjects repeated measurements, linear mixed effects regression will be used to determine the effect of treatment condition on the IPF values (spontaneous and resting state open), with a random intercept for the subject factor. Subject age, gender, blink sequence (the order of the blink recorded in the video), and the order of interventions (whether evaluated in the first or the second arm of the crossover) will be covariates of interest. Effect of each covariate will be investigated alone, and only statistically significant ($P < .05$) covariates will be included in the final regression model, from which, the estimated marginal means and their 95% confidence interval (CIs) will be reported for each of the outcomes. Missing values at the T2 time point will be imputed from another time point within the same subject (T1 by default or T0 if both T1 and T2 were not available). For volitional blinks, a test of proportionality will be performed to determine the effect of the 3 treatments on the probability of eye not fully closing.

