10.4.2 Analysis of the Primary Efficacy Endpoint(s)

We will use a repeated measures mixed effects model for analysis of the primary outcome measure (change in interpalpebral fissure during opening and spontaneous blinking). The model will include a random subject-level intercept and a fixed treatment effect (MLP or KTFS). A repeated measures model will be used with primary timepoint for analysis being after 1 week of use. . The model will also include fixed effects of treatment order (i.e., MLP: KTFS vs KTFS:MLP), and crossover period (period 1 or 2), and will control for age and sham opening interpalpebral fissure.

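### The primary analysis is specified in two incompatible ways, opening fissure is secondary in one place and primary in others, and no success rule is given

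*Combined protocol and SAP*

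**What the plan says.** **Model.** Section 10.2, under its primary-outcome label, takes as response "the IPF values (spontaneous and resting state open), with a random intercept for the subject factor". Its candidate covariates are age, gender, "blink sequence (the order of the blink recorded in the video") and a period term: "the order of interventions (whether evaluated in the first or the second arm of the crossover) will be covariates of interest". The selection rule follows: "Effect of each covariate will be investigated alone, and only statistically significant" terms (P<.05) enter the final model. Results are then given per measure: "the estimated marginal means and their 95% confidence interval (CIs) will be reported for each of the outcomes".

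Section 10.4.2 analyses the "primary outcome measure (change in interpalpebral fissure during opening and spontaneous blinking"). It always includes a subject intercept, treatment, treatment order "and crossover period (period 1 or 2), and will control for age and sham opening interpalpebral fissure". It names neither gender nor blink sequence. Neither section says that it governs.

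**Endpoint.** The Summary reads "Primary outcome: Difference between MLP and KTFS in the change in interpalpebral fissure during and spontaneous blinking", apparently with a word missing, and lists opening with volitional blinking as secondary. Section 4.2.1 makes opening and spontaneous blinking primary, with a difference of at least 1 mm. Sections 10.2 and 10.4.2 also treat both measures as primary, and 10.4.3 leaves only volitional blinking as a secondary fissure measure.

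**Decision rule and timing.** Section 10.4.9 says p-values will be corrected where appropriate and that no multiple comparisons are planned. Section 10.5 gives N=16 at power 0.80 for a single primary outcome, after effects were examined in 8 completers. Section 10.4.7.2 adds periodic preliminary analyses. Section 10.6.1 provides a masked analyst and letter codes for allocation.

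**The concern.** Age and period cannot be both conditional and mandatory, so 10.2 and 10.4.2 cannot be read as a summary and its detail. Two analysts following different sections would fit different models, possibly on different outcome scales. Two readers could also disagree on whether the trial had succeeded: on opening alone, spontaneous blinking alone or both, and against zero or against 1 mm. Because effects were seen after 8 completers and further looks are planned, an open choice of model, endpoint and rule could be settled with knowledge of the data.

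There is also a gap that the two sections share. Blink order as a covariate implies several blinks per recording, yet the only random term named in either section is a subject intercept.

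**Working it through.** **1. The two models side by side**

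| | 10.2 | 10.4.2 |
|---|---|---|
| Response | fissure values | change in fissure |
| Period | only if P<.05 alone | always |
| Age | only if P<.05 alone | always |
| Gender, blink sequence | only if P<.05 alone | not named |
| Treatment order | not named | always |
| Sham opening fissure | not named | always |
| Random term | subject intercept | subject intercept |

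With complete pairs, covariates that are constant within a subject (age, gender, treatment order, one sham value) hardly move the MLP-KTFS contrast. Period is the covariate that can. Values and change give the same contrast if each subject has one baseline. They differ if each period has its own, which 7.3.2 makes possible by taking baseline measures during training.

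**2. The stated N.** Section 10.5 gives N=16 and power 0.80, with 0.05 called both alpha and a type II error. It gives no effect, SD, sidedness or test, so 16 cannot be reproduced. Assuming a paired two-sided 0.05 t-test on one measure, solving the noncentral t for 0.80 power at n=16 (15 df) gives a standardized difference of 0.749. The normal approximation gives (1.960+0.842)/√16 = 0.700.

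**3. Requiring both measures.** Assume equal effects of 0.749. If the measures are independent, joint power is 0.80 × 0.80 = 0.64. By simulation at N=16:

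| Correlation | Joint power | Smallest N for 0.80 |
|---|---|---|
| 0 | 0.64 | 21 |
| 0.3 | 0.66 | 20 |
| 0.5 | 0.68 | 20 |
| 0.8 | 0.73 | 19 |

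Alpha is kept under this rule.

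**4. The period screen.** Let the within-subject difference have SD about 1.33 mm (1 mm / 0.749, an assumption used only to set a scale) and let the true device difference be 1 mm. With n1 MLP-first and n2 KTFS-first completers, and period 2 higher by π, omitting period shifts the estimate by -π(n1-n2)/(n1+n2). At 8:8 this is zero. At 10:6 it is -π/4: -0.125 mm for π=0.5 and -0.25 mm for π=1. Screening omits period only in some runs (about 96% and 64% respectively), so the average shift is smaller than those values at -0.11 and -0.13 mm.

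| Split | π (mm) | Power, period kept | Power, screened | Mean bias, screened (mm) |
|---|---|---|---|---|
| 8:8 | 0.5 | 0.79-0.80 | 0.78-0.79 | 0 |
| 8:8 | 1 | 0.79-0.80 | 0.78 | 0 |
| 10:6 | 0.5 | 0.77 | 0.66 | -0.11 |
| 10:6 | 1 | 0.77 | 0.59-0.60 | -0.13 |

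The 10:6 rows take the unfavourable direction; with the split or the period effect reversed, the shift is upward. Type I error stays near 0.05 throughout.

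**5. Cost of always keeping period.** The adjusted estimate has variance (σ²/4)(1/n1+1/n2). At 8:8 this is σ²/16, as without adjustment, so only one degree of freedom is lost and power is 0.796. At 6:10 it is 0.0667σ² against 0.0625σ², and power is 0.770.

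**6. Blinks.** If single blinks are analysed with only a subject intercept, blinks from one subject in one period are treated as independent given the subject. Any subject-by-period variance then makes the standard error of the device contrast too small, and type I error exceeds 5%. With no such variance, or with one mean per subject and period, it stays at 5%. The documents give neither blink counts nor variance components, so the excess cannot be sized from them.

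**The case against.** The period screen is the weakest part: at 8:8 it causes no bias and almost no power loss, and the 10:6 split is assumed. That stands, and the case does not depend on it. Most of the other differing covariates are constant within a subject and hardly affect the contrast; that stands too. The Summary line has probably lost a word, and the other sections agree with one another. But restoring opening there would make it both primary and secondary in the Summary, so a correction is still needed. Masking of the analyst and the letter codes reduce the risk of a data-driven choice. They do not remove it once effects have been measured and N cut on them.

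Several stronger inferences are tempting but unsupported:

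- **That the stated power of 0.80 is false, or valid for only one measure.** Section 10.5 gives no effect, SD or test, and N could have been sized on a joint rule.
- **That the family-wise error is inflated because either measure may succeed.** No section states that rule, and the wording of 4.2.1 leans towards requiring both.
- **That the 1 mm threshold makes success improbable.** No section proposes a confidence-limit criterion, and any such percentage would assume that N was sized on 1 mm, whereas 10.5 cites the interim effects.
- **That the blink analysis has a specific, large type I error.** Both sections speak of repeated measures without giving the full covariance structure, and a figure would need inputs the documents lack.

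**Conclusion.** Wrong as written. The contradictions between 10.2 and 10.4.2, and between the Summary and the other sections, are textual and need no assumed number. So are the absence of a one-or-both rule, of a stated role for 1 mm and of a usable multiplicity rule. Correction is needed because the primary result is not tied to one endpoint, model and criterion after an interim look at effects.

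The size is conditional. The joint power of about 64% to 73% assumes a paired two-sided 0.05 test, 0.80 power for one measure at N=16 and equal effects. The period-screen figures assume one value per subject and period and the SD, period effects and splits shown. Power as now stated cannot be verified either way.

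**What to change.** 1. Delete the P<.05 covariate screen from 10.2. Make the 10.4.2 model, with period and treatment order always included, the single primary model, on one outcome scale worded identically in both sections.
2. State how blinks enter: one mean per subject, period and measure, or a subject-by-period random effect in the model.
3. Name the same primary measure(s) in the Summary, 4.2.1, 10.2 and 10.4.2. Replace the 10.4.9 wording with one rule: a single primary, both required, or Holm at overall 0.05. Say whether 1 mm is a planning value or a success criterion and, if the latter, whether it applies to the estimate or to a confidence limit.
4. Restate power for N=16 under that rule, with the effect, SD and test used. Date the choice relative to the 8-completer interim analysis, and fix it before the letter codes are opened.

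**Cost.** The change is to wording plus one power calculation, with no new visits or procedures. Always keeping period costs about 0.004 power at 8:8 and 0.03 at 6:10. If both measures stay primary and both are required, the stated power becomes less favourable, or N rises to 19-21 to hold 0.80 under the assumptions above. Holm gives per-measure power of about 0.75 to 0.77 with equal effects, and about 0.69 if the other measure has no effect.

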7.3.2 CROSSOVER

After consent and enrollment, subjects will be randomly assigned to one of the two arms for the crossover period. In one arm subjects will receive the MLP first and the KTFS second. In the other arm, subjects will receive the KTFS first and the MLP second.

Each period of the crossover will last for about three weeks, including about two weeks of training in how to apply and remove the device followed by about one week of using the device at home. Training will be conducted at study visits at Mass Eye and Ear. Typically there will be two training visits. Baseline measures of eye lid blinking without and with the device will be taken during training. For the MLP, two baseline measures of eye lid blinking will be recorded one with the real MLP device and one with a sham MLP device to determine how much improvement might occur simply through a placebo effect. However, for the KTFS it will not be possible to take a baseline measure with a sham KTFS. Only subjects and caregivers who demonstrate sufficient ability to apply and remove the device will be permitted to take it home. During the period of home wear, there will be a video call every other day to monitor the subject’s use of the device and safety. During the kfts arm, an occupational or physical therapist consulting with the Massachusetts eye and ear study team may talk with the subject during the video conference call to ensure that the kinesio tape is in the correct position. Mass General Brigham approved software will be used for video calls. During the trial week of home use of devices, subjects will

also receive REDCap survey link notifications each day to complete a brief survey to log if they are wearing the device (see the detailed plan above, and see attached document for survey language and questions).

To ensure no carry-over effects, there will be a washout of about 2 weeks duration between the first and second period of the crossover during which subjects will not be permitted to use any device for their blepharoptosis. (This will be similar to their habitual state before enrollment since none of the participants would have been using any device for their blepharoptosis about two weeks before enrollment).

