7.3.7 Schedule of Events Table

*Visits 8-10 are in office, approximately every second week. There will be video

		Consent	EQ-5D-5L Questionnaire	aQoL Questionnaire	GBI Questionnaire	Visual Acuity	SlitLamp, skin rating, & NEI grading	Video Recordings & Comfort ratings	Application & Removal training	Debrief and device comparison questionnaire	Clinical decision
Device 1	Visit 1	x	x	x		x	x	x	x		
	Visit 2					x	x	x	x		
		About 1 week wearing at home with video calls for safety monitoring and daily survey about wear time									
	Visit 3		x	x	x	x	x	x			
	Washout (about 2 weeks)										
Device 2	Visit 4		x	x		x	x	x	x		
	Visit 5					x	x	x	x		
		About 1 week wearing at home with video calls for safety monitoring and daily survey about wear time									
	Visit 6		x	x	x	x	x	x			
	End of crossover period										
	Phone call									x	
	Visit 7					x	x	x			x
	Start of extended wear trial (about 6 months)										
Chosen device											
	Visit 8		x	x	x	x	x	x			
	Long term follow up										
	6 month phonecall		x	x	x						
	12 month phonecall		x	x	x						

call follow ups on weeks without an in-office visit

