8 ASSESSMENT OF SAFETY

8.1 Specification of Safety Parameters

The safety of the study devices will be evaluated at every visit following the enrollment visit and will be defined by the incidence of related adverse events. Specifically, we will evaluate:

10. **Systemic safety:** Incidence and severity of systemic adverse events during the study (adverse events spontaneously reported or observed by the Research Assistant).
11. **Ocular safety:** Incidence and severity of ocular adverse events during the study (ophthalmic examination, adverse events spontaneously reported).

SAFETY CUTOFFS: Serious adverse events which would result in study suspension: Should visual acuity decrease more than 2 lines, worsening of corneal rating of more than 1.5 points or other ocular surface ratings more than 2 points, and comfort rating lower than 5/10; study activities will cease for at least 1 week and an adverse event report will be sent to the IRB. Corneal rating changes >1.5 points will be reviewed by the independent safety monitor at the Eye and Ear to determine if criteria for study suspension or dismissal are met, and when it may be possible to continue. Serious adverse events which will result in immediate dismissal from the study (and treatment) include: 1) development of a related corneal ulcer (as judged clinically by the independent safety monitor) with or without infiltrate or 2) broken skin on the eyelid (skin decompensation).

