10.3 Analysis Datasets

The dataset for the analysis of the primary outcome measure will be an intention-to-treat dataset.

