10.6 Measures to Minimize Bias

10.6.1 Masking AND RANDOMIZATION Procedures

Masking:

Subjects will be masked as to which of the two devices is the new treatment. They will simply be told that they are evaluating two non-surgical treatments for blepharoptosis. A debriefing questionnaire will be administered after the second period of the crossover to determine whether subjects guessed that the MLP was the new treatment and the KTFS was the comparison treatment.

Data assessors (e.g. Turkers) for the primary outcome will be masked since they will not be familiar with the study or the 2 treatments. They will review videos of blink dynamics which have been cropped to show only the eye region so the subject cannot be identified (see Measurements of Eye Lid Kinematics in section 10.4.1).

The person conducting statistical analyses of the primary outcome will be masked.

It is not possible to mask the study team member who will fit and provide training for the MLP device, since the fitting requires specialist expertise. That study team member will avoid telling subjects that the MLP is the new treatment. Furthermore the quantification and analysis of the primary outcome will be conducted by masked data assessors.

A person external to the study team will fit and provide training for the KTFS. Again, it will not be possible to mask this person. However, this person is highly experienced in using Kinesio Tape, a proponent for its use for blepharoptosis, and has received training in fitting Kinesio Tape for ptosis. Again they will avoid telling subjects that the KTFS is the comparison treatment, and the quantification and analysis of the primary outcome will be conducted by masked data assessors.

Recruitment for the clinical trial has been very successful so far. However the greater number of subjects than initially anticipated means that we have been running into problems when trying to schedule visits with the Physical Therapy Team Member (PT) for fitting of the kinesiotape frontalis sling (KTFS). The PT sometimes does not have sufficient room in her clinic schedule to accommodate a taping visit per the schedule in the protocol. We've described a backup plan below to ensure that participants receive taping visits per the original protocol schedule even when the PT is not available. Please note that the proposed plan requires that the PT will provide oversight of all taping visits by reviewing videos of the taping sessions.

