As a backup plan in case scheduling constraints mean that it is not possible to schedule a taping visit with the PT:

1. The PI will perform the tape placement.
2. The PI or the research staff will be in attendance as the participants practice placing the tape.
3. The entire process will be recorded and the video loaded onto a secure server or shared via Institutional DropBox
4. The PT will be responsible for reviewing the videos within two days of placement, to ensure proper technique.

Randomization

Participants will be assigned to one of two possible treatment allocations: 1) MLP then KTFS or 2) KTFS then MLP. The allocation will be performed using software that implements the process of minimization. The first participant will be assigned randomly with each subsequent participant assigned in such a way as to approximately balance the number of participants who are 65 years of age and over and who have acute vs chronic ptosis. We propose to balance for these two factors because adults over the age of 65 typically have thinner and looser eyelid skin, and participants with acute ptosis may recover while enrolled in the study, which may affect outcomes. Letter codes, randomly assigned to each of the treatment allocations by a researcher external to the study will be used by the software. The code breaker will be kept in a sealed envelope in a location known only to the external researcher. Data provided to the masked data assessors and the masked person conducting statistical analyses will use the letter codes to identify treatment allocation.

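### A missing T2 value, most plausibly the 1-week primary value, is filled from an earlier recording whatever the reason; this biases the device contrast if share filled times change in lift differs between devices

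*Combined protocol and SAP*

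**What the plan says.** Section 10.2 sets the missing-data rule: "Missing values at the T2 time point will be imputed from another time point within the same subject (T1 by default or T0", T0 being the fallback when T1 is also absent. The filled value enters the model like any other, and no allowance for its being imputed is described.

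Section 10.4.2 fixes the target: "A repeated measures model will be used with primary timepoint for analysis being after 1 week of use". Section 10.3 adds: "The dataset for the analysis of the primary outcome measure will be an intention-to-treat dataset". It does not say how a device that could not be used is scored.

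The readable text does not say which visits T0, T1 and T2 are; the study schema is not shown and may do so. Section 7.3.2 places the baseline recordings, without and with the device, in training. The table in section 7.3.7 has video at Visits 1 and 2 (device 1) and 4 and 5 (device 2), then a home week ("About 1 week wearing at home with video calls for safety monitoring and daily survey about wear time"), then video at Visits 3 and 6. T2 as Visit 3 or 6 is therefore the natural reading.

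Two provisions could leave that visit without a value for device-related reasons. Section 7.3.2: "Only subjects and caregivers who demonstrate sufficient ability to apply and remove the device will be permitted to take it home". Section 8.1: "Serious adverse events which will result in immediate dismissal from the study (and treatment) include" a related corneal ulcer or broken lid skin. Under section 5.4.2, participants who withdraw early are asked only for a closing telephone call.

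**The concern.** The estimate is meant to describe lift after a week of use. A filled value describes lift before home use and is analysed as if it had been observed at one week. That is harmless if lift is stable between the two recordings, or if the effects cancel between devices.

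The protocol gives some reason to doubt stability. Section 10.6.1 warns that "participants with acute ptosis may recover while enrolled in the study, which may affect outcomes". It also has specialists fit each device at training (for the tape: "A person external to the study team will fit and provide training for the KTFS"), whereas participants or caregivers apply it at home. Nor need a lid magnet and a tape sling lose the same number of 1-week values. If lift falls after training, the fill favours the device with more filled values; if lift rises, the sign reverses.

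**Working it through.** **1. The plan's own figures.** Section 10.5 first planned 40 completers plus 10 for attrition, and 40 + 10 = 50 agrees with the stated total. The final 16 (power 0.80, alpha 0.05) cannot be reproduced, because neither an SD nor a target difference is given. Solving backwards with a paired t-test, two-sided alpha assumed, n = 16 and power 0.80 imply a standardised effect of 0.749. A 1 mm target then implies an SD of 1/0.749 = 1.33 mm and an SE of 1.33/√16 = 0.33 mm.

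**2. Shift caused by the fill.** With 16 analysed (section 10.5),

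shift = (number filled on A × fall on A − number filled on B × fall on B)/16,

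where the fall is T1 lift minus T2 lift in the filled participants. The numbers filled and the falls are assumptions; the documents give none.

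| Filled, A v B | Fall 1 mm on both | Fall 2 mm on both |
|---|---|---|
| 1 v 0 | 1/16 = 0.06 mm | 2/16 = 0.125 mm |
| 2 v 0 | 2/16 = 0.125 mm | 4/16 = 0.25 mm |
| 2 v 1 | (2 − 1)/16 = 0.06 mm | (4 − 2)/16 = 0.125 mm |
| 2 v 2 | 0 | 0 |

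With no fall, every entry is zero. Equal missingness protects only if the falls are also equal: with 20% filled on each device and a 1 mm fall on one device only, the shift is 0.20 × 1 = 0.20 mm. The reference is the 1 mm difference in section 4.2.1.

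**3. Effect on intervals.** Simulation with n = 16, paired t, 40,000 runs and assumed SDs of 1.0 mm (subject), 0.7 mm (subject by device) and 0.5 mm (visit), so that the paired difference has SD √(2 × (0.49 + 0.25)) = 1.22 mm. Missingness is unrelated to lift, and everyone has the same fall.

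- 2 v 0 filled, falls of 0, 1 and 2 mm: bias −0.002, 0.126 and 0.252 mm; coverage 95.1%, 94.1% and 92.5%.
- 1 v 0 filled, falls of 1 and 2 mm: bias 0.062 and 0.124 mm; coverage 95.2% in both.
- 2 v 1 filled, falls of 1 and 2 mm: bias 0.064 and 0.126 mm; coverage 95.7% and 97.5%.

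**4. Mixed model on observed recordings.** Same assumptions, 2 v 0 missing, with device-by-visit means and random subject and subject-by-device effects (5,000 runs). For falls of 0, 1 and 2 mm, bias is −0.002, −0.005 and 0.001 mm and coverage 95.7%, 95.4% and 95.6%. With no fall, the mean SE is 0.307 mm against 0.299 mm for the fill, a ratio of 1.03.

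**5. When the missing participants are the failures.** Suppose only the two participants with missing values lose lift, by 1, 2 or 3 mm. The fill keeps their earlier lift, so it is wrong by 2 × 1/16, 2 × 2/16 and 2 × 3/16 = 0.125, 0.25 and 0.375 mm. The mixed model predicts their week-1 lift from their earlier recordings and from participants who did not lose lift. Simulation gives it the same bias: 0.125, 0.250 and 0.375 mm.

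**6. Size relative to the SE.** The implied SE scales with the target. For targets of 1, 2 and 3 mm it is 0.33, 0.67 and 1.00 mm, so 0.25 mm is 0.75, 0.37 or 0.25 SE.

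**The case against.** The case for leaving the rule alone has substance.

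- **The harm is small in most scenarios.** Coverage stays near or above 95% with 1 v 0 or 2 v 1 filled, and is about 94% with 2 v 0 and a 1 mm fall. It reaches 92.5% only with a fall of twice the endpoint. This stands and limits the severity.
- **There are safeguards against a fall.** Section 7.3.2 requires demonstrated ability before home use, has video calls every other day, and lets a therapist check tape position. No passage says who applied the device at any given recording. Recovery of acute ptosis is not specific to a device, and minimisation balances acute and chronic cases across sequences. All this makes a large, unequal fall less likely but does not exclude one.
- **The routes to a missing value are inferred.** Section 7.3.2 does not cancel Visit 3 or 6 for someone who cannot take the device home. Dismissal in period 1 also removes the second device's data. This stands.
- **The fill may serve another purpose.** Section 10.2 speaks of 3 treatments, and section 7.3.2 describes the sham recording only as a training baseline. The rule may partly supply a sham value where no 1-week sham recording is described. This cannot be settled from the readable text, so the proposed change is confined to the MLP and KTFS 1-week values.
- **The mixed model is not a cure.** A reader might infer from step 4 of the working that it removes the bias. It does so only when missingness is unrelated to the unseen 1-week lift. Under device failure, the very route sections 7.3.2 and 8.1 suggest, step 5 shows it is as biased as the fill.

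**Conclusion.** The point holds in conditional form. The rule is unconditional, no sensitivity analysis accompanies it in sections 10.2 to 10.4, and on the natural reading it puts a pre-home-use value in place of the primary 1-week value. Under the assumed 2 v 0 pattern with a 1 to 2 mm fall, the shift is 0.125 to 0.25 mm. It is zero if lift is stable or if the effects cancel. Severity is minor to moderate.

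Three stronger readings are not supported:

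- **That the rule does distort the result, or favours the MLP.** The documents give no missing shares by device, no change in lift and no direction.
- **That the shift is three quarters of a standard error.** This assumes the 16 targets 1 mm. Section 10.5 ties the reduced number to effects seen in interim analyses, which points to an observed effect instead; hence the range of 0.25 to 0.75 SE.
- **That the bias reaches 0.25 to 0.5 mm.** That figure (2/16 × an assumed training lift of 2 to 4 mm) comes from scoring failures as no lift. Sections 4.2.1 and 10.4.2 do not specify that estimand, so it is not bias against the stated endpoint.

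**What to change.** 1. For the MLP and KTFS 1-week values, drop the T1/T0 fill. Fit the planned mixed model to observed recordings, with device-by-visit terms, and estimate the contrast at the 1-week visit. The figures in step 4 also rest on a subject-by-device random effect; section 10.4.2 names only a subject intercept.
2. Prespecify one sensitivity analysis, labelled as a different estimand, that sets the change to zero for participants who could not take the device home or were stopped for a device-related event. This is the part that addresses device failure.
3. Map T0, T1 and T2 to visit, device and condition in the text, including which recording serves as sham. The map also matters for the fallback: if T0 were a recording without the device, filling from it would enter no lift. Report missing 1-week values by device and reason.

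The cost is SAP wording, one extra analysis on data already collected, and an SE about 2 to 3% larger in the simulated case with no fall. The main and sensitivity results may differ, and both must be reported. No visit or clinical rule changes.
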